# 8.4. Exploratory Endpoints

The exploratory endpoints are the following: Total number of RSV-associated medical visits (hospital, ER, UC, or pediatric visitsa) for each subject and associated treatments or procedures at these visits

- Total number of medical visits (hospital, ER, UC, or pediatric visitsa) for each subject and associated treatments or procedures at these visits, during the study period excluding the initial RSV-associated medical visits.
- Number of RSV-confirmed hospitalizations (defined as stay in hospital [or its ER] for 24 hours or longer)
  - Number of days with RSV-associated mechanical ventilation
  - Number of days with RSV-associated supplemental oxygen
- Length of stay in hospital for RSV-associated illness

<sup>a A pediatric clinic visit represents any outpatient medically attended visit that could include, but is not limited to, a pediatric clinic visit, a primary physician office visit, a family physician visit, or a study site visit.

- Number of missed days of work for parent(s) or guardian(s) associated with each medically attended RSV event
- Number and proportion of subjects with other common respiratory pathogens identified by a RT-PCR multiplex respiratory panel which is distinct from the RT-PCR assay being used to test for RSV for the study's efficacy endpoints.

Note: Only nose swab specimens determined to be negative for RSV using the RT-PCR assay being utilized for evaluation of the study's efficacy endpoints will be evaluated by the RT-PCR multiplex respiratory panel. RSV positive samples identified by the RT-PCR multiplex respiratory panel will not be taken into account for the purpose of the analysis of the study's efficacy endpoints.

a A pediatric clinic visit represents any outpatient medically attended visit that could include, but is not limited to, a pediatric clinic visit, a primary physician office visit, a family physician visit, or a study site visit.

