# 9.2. Sample Size

For Part A, the goal of the study is to study infant PK, and therefore no formal sample size calculation will be conducted.

For Part B, the sample size estimation is based on the primary efficacy endpoint of medically attended RSV infection (hospitalization or outpatient LRTI). Literature (Hall 2009, Ambrose 2014) show that the event rate in this endpoint is in the range of 12% to 22% in the studied infant populations. As the event rate may vary over RSV season or geographic region, it is assumed that event rate is 10% for the placebo group, and either dose of RENG2222 would reduce the event rate from placebo by 60% (event rate of 4%). With 505 randomized subjects per arm or a total of 1515 randomized subjects, the study has 90% power to demonstrate a 60% or greater reduction at 2-sided significance level  $\alpha$ =0.025. This sample size also incorporated a 5% early dropout rate. The sample size calculation is based chi-square test with continuity correction and performed using nQuery version 7.0 (Statistical Solutions Ltd, Cork, Ireland).

The significant level of 2-sided 0.025 is set in consideration of multiplicity of 2 comparisons between each of the 2 REGN2222 dose arms with placebo.

With a total of 1515 randomized subjects and 1:1:1 randomization ratio, it is expected 1010 subjects to receive REGN2222 (505 subjects in each of the 2 REGN2222 arms) and 505 subjects to receive placebo and in total, an approximate of 90 primary endpoint events. Also, with 1010 subjects exposed to REGN2222, the regulatory requirement for safety assessment will be met.

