2.2. Sample Size and Power Considerations

Originally Planned Sample Size

For Part B, the sample size estimation is based on the primary efficacy endpoint of medically attended RSV infection (hospitalization or outpatient LRTI). Literature ([Hall 2009](#), [Ambrose 2014](#)) show that the event rate in this endpoint is in the range of 12% to 22% in the studied infant populations. The Hall data is population based and the majority of infants are full-term; the Ambrose publication of data from the RSV Respiratory Events Among Preterm Infants Outcomes and Risk Tracking (REPORT) study evaluated preterm infants of 32-35 weeks gestational age and less than 6 months of chronological, whom were not receiving RSV prophylaxis. As the event rate may vary over RSV season or geographic region, a relatively conservative approach was taken to assume that event rate is 10% for the placebo group, and either dosing regimen of REGN2222 would reduce the event rate from placebo by 60% (event rate of 4%). With 505 randomized subjects per arm or a total of 1515 randomized subjects, the study would have 90% power to demonstrate a 60% or greater reduction at 2-sided significance level $\alpha=0.025$. This originally planned sample size also incorporated a 5% early dropout rate. The sample size calculation was based on chi-square test with continuity correction and performed using nQuery version 7.0 (Statistical Solutions Ltd, Cork, Ireland).

Based on the originally planned sample size and event rate assumption, we anticipated approximately 90 primary endpoint events.

The blinded sample size re-estimation (as detailed in the study protocol Section 9.2.1) designed for the originally planned sample size has not been performed for this study.

Power Calculation for Reduced Sample Size

[figure not shown]
The sample size of the study has been reduced due to business considerations. The intent of this power calculation is to understand the impact of the reduced sample size on the primary efficacy analysis. Specifically, to accommodate the reduced sample size, the overall Type I error for the pairwise comparisons of each REGN2222 dose regimen to placebo will be controlled using a

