- 14) Repeat items 9) through 13) above with the single exception to count the number of all-cause respiratory illness-associated visits **after** the initial episode of RSV illness.
- 15) Total number of days with RSV-associated mechanical ventilation for subjects with RSV-confirmed hospitalizations.
- 16) Total number of days with RSV-associated supplemental oxygen for subjects with RSV-confirmed hospitalizations.

- 17) Total length of stay in hospital for subjects with RSV-confirmed hospitalizations.
- 18) Total number of missed days of work for parent(s) or guardian(s) associated with each medically attended RSV event.
- 19) Number and prevalence rate of other common respiratory pathogens identified by a RT-PCR multiplex respiratory panel for nose swab specimens determined to be negative for RSV (using the protocol specified Lyra RT-PCR assay [Quidel Molecular RSV/hMPV assay]).
- 20) Proportion of FAS subjects with the primary endpoint event, with the single exception of using an alternative definition for LRTI.

Instead of the LRTI definition in Section 4.6.1, the following definition of LRTI will be used for medically attended RSV infection (hospitalization or outpatient LRTI) as agreed in the Pediatric Investigational Plan (PIP) :

Infant with RSV-proven infection who presents with cough or difficulty breathing **and 2** of the following criteria:

- Lower chest wall indrawing
- Hypoxemia (peripheral capillary oxygen saturation <95% breathing room air)
- Wheezing or crackles
- Ventilatory failure (needing ventilator support in any form)
- New onset apnea
- Increased respiratory rate using WHO criteria for fast breathing for age ([Wingerter 2012](#)) as below:

| Age | Increased Respiratory Rate (breaths/min) |
|--------------------|------------------------------------------|
| < 60 days | ≥ 60 |
| 60 - 364 days | ≥ 50 |
| 365 days - 5 years | ≥ 40 |

Age in days = Onset date of the episode of RSV illness – birth date +1.

- 21) Proportion of FAS subjects with the primary endpoint event, with the single exception of the removal of RSV hospitalization non-LRTI.
- 22) Proportion of FAS subjects with the primary endpoint, with the single exception of accepting positive RSV detection results from the multiplex RT-PCR respiratory panel in deriving the primary endpoint event.

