5.7.4. Analysis of Exploratory Efficacy Variables

Time to event endpoints

Number of days to the first efficacy endpoint event will be analyzed with stratified log-rank test. Different from the primary analysis, this time to event analysis will treat missing primary endpoint at Day 150 visit through a censoring method as described in Section 4.6.3.

The SAS LIFETEST procedure will be used to run the stratified log-rank test by specifying region and gestational age category in the STRATA statement as 2 stratifying variables, and specifying treatment group in the GROUP= option. In addition, for each treatment group, Kaplan-Meier curve will be used to graphically depict the proportion of subject who remained event free across time during the 150-day efficacy assessment period. Cox regression will be used to obtain hazard ratios and their confidence intervals. The Cox regression model will include the fixed categorical effects of treatment group, region, and gestational age category.

Continuous efficacy endpoints

Descriptive statistics including the number of subjects reflected in the calculation (n), sum, mean, median, SD, minimum, Q1 and Q3, and maximum will be used to summarize the continuous exploratory endpoints (eg, total number of medical visit, length of stay in hospital, etc., as defined in Section 4.6.3) for each treatment group and their treatment difference between each REGN2222 arm and placebo. For each exploratory endpoint, this descriptive summary will include only those subjects who had at least 1 endpoint specific event.

To account for subjects who had no endpoint specific event, a separate analysis will be performed for each exploratory endpoint to include these subjects by treating their endpoint value as zero. In this analysis, the event rate adjusted by subject-year of follow-up will be provided for each treatment group. For each subject, the duration calculated as (end of efficacy evaluation - first dose date +1)/365.25 will be counted toward the subject-year of follow-up, except that for the endpoint of total number of respiratory illness-associated hospital, ER, UC, or PC visits **after** the initial episode of RSV illness, the duration will be (end of efficacy

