evaluation - the day after the stop date of the initial episode of RSV illness + 1)/365.25. The end of efficacy evaluation is the last visit completed by a subject, scheduled or unscheduled, up to Visit 7. Negative binomial regression will be used to estimate the relative risk reduction associated with each REGN2222 arm as compared to placebo.

Categorical efficacy endpoints

RSV confirmed hospitalization, a component of the primary composite endpoint, will be explored using the same statistical methodology as the primary efficacy analysis. For this exploratory analysis, the two REGN2222 treatment groups will be combined for comparison to the placebo group, with the intent to evaluate the REGN2222 effect on subjects with RSV confirmed hospitalization.

Number and percentage of subjects taking medications associated with RSV or respiratory illness will be summarized by treatment group. The denominator used to calculate percentage will be the number of subject in the FAS assigned to each treatment group. The tables will be sorted by alphabetical order of ATC level 2 followed by ATC level 4.

The procedures associated with RSV or respiratory illness will only be listed for subjects in each treatment group.

The same CMH statistics as used in the primary approach for the primary efficacy variable will be used to analyze the following exploratory endpoints. Missing data will be addressed using the same same rules as used in the primary analysis for the primary efficacy variable (Section 4.6.1).

- Proportion of FAS subjects with the primary endpoint event, with the single exception of using an alternative definition for LRTI.
- Proportion of subjects with the primary endpoint event, with the single exception of the removal of RSV hospitalization non-LRTI

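### The analysis of visits after the initial RSV episode has no defined follow-up for RSV-free infants, so its relative risk reduction may restate RSV prevention or rest on an infected-only subset

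*SAP*

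**What the plan says.** SAP 4.6.3 item 14 repeats the preceding all-cause respiratory items "with the single exception to count the number of all-cause respiratory illness-associated visits" that fall after the initial episode of RSV illness. It does not restrict the endpoint to infants who had such an episode.

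SAP 5.7.4 plans a separate analysis of each exploratory count for subjects without the event in question, "to include these subjects by treating their endpoint value as zero". Follow-up normally runs from first dose to the last visit completed, up to Visit 7. For item 14 that rule is replaced: follow-up is the end of efficacy "evaluation - the day after the stop date of the initial episode of RSV illness + 1)/365.25". Negative binomial regression then estimates a relative risk reduction for each REGN2222 arm against placebo. The section names no start date for an infant without an RSV episode, does not say whether such infants are excluded, and does not state the offset.

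Protocol 8.4 words the corresponding endpoint differently: the total number of medical visits per subject, "during the study period excluding the initial RSV-associated medical visits". SAP 1.2.3 records no modification from the protocol's statistical section. SAP 5.7.3 makes p-values outside the testing hierarchy descriptive.

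**The concern.** The zero rule and the follow-up rule cannot both be applied to an RSV-free infant. One keeps the infant in with a count of zero; the other gives no time at risk. At the planning rates this concerns about 90% of placebo and 96% of REGN2222 infants.

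An infant without RSV cannot have a visit after an RSV episode, so the zero is structural. An arm with fewer RSV episodes then has fewer countable visits even if the drug does nothing once an episode is over. A relative risk reduction in later respiratory visits could be read as benefit beyond preventing the first episode. SAP 8 says the first-step analysis will be used to plan a separate efficacy study and to communicate with health authorities, so an exploratory figure of this kind may be acted on.

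**Working it through.** **Inputs from the documents.** SAP 2.2 says the planners chose to "assume that event rate is 10% for the placebo group", with a 60% reduction to 4% on REGN2222. It cites a literature range of 12% to 22%. The efficacy period is 150 days. About 1200 treated infants at 1:1:1 gives 400 per arm.

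**Checking the planning rates.** The documents give no figure for item 14, so I first confirmed that 10% and 4% are the rates behind the stated sample size. Protocol 9.2 sets alpha as follows: "The significant level of 2-sided 0.025 is set in consideration of multiplicity of 2 comparisons".
- Uncorrected: n₀ = [2.241·√(2·0.07·0.93) + 1.282·√(0.10·0.90 + 0.04·0.96)]² / 0.06² = 447.
- Continuity-corrected: n = (n₀/4)·[1 + √(1 + 4/(n₀·0.06))]² = 480.
- Dropout of 5%: 480/0.95 = 505.3, against 505 stated.
- Events: 505 × (0.10 + 0.04 + 0.04) = 90.9, against about 90 stated.
- Power at two-sided 0.05 with 380 per arm (400 less 5%): 87.4%, against about 87% stated.

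**Set-up for item 14.** Assume the drug has no effect on visits after an RSV episode. Let p_c and p_t be the proportions with an RSV episode on placebo and REGN2222, F = 150 days, and m the mean follow-up after the episode. The documents do not give m; I took 75 days, with a range of 40 to 110.

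**(a) RSV-free infants kept as zeros with 150 days each.** The later-visit rate cancels, leaving

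RR = {p_t·m / [(1−p_t)F + p_t·m]} ÷ {p_c·m / [(1−p_c)F + p_c·m]}.

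- REGN2222: 0.04 × 75 = 3, and 3/(144 + 3) = 0.02041.
- Placebo: 0.10 × 75 = 7.5, and 7.5/(135 + 7.5) = 0.05263.
- RR = 0.388, an apparent reduction of 61.2%.

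For placebo rates from 5% (assumed) to 22%, a 60% RSV effect and m from 40 to 110 days, the reduction runs from 60.3% to 64.1%.

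**(b) Zeros kept, no offset.** RR = p_t/p_c = 0.04/0.10 = 0.40, a reduction of exactly 60%.

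**(c) RSV-free infants dropped because duration is missing.** The expected RR is 1, but it rests on 400 × 0.10 = 40 placebo and 400 × 0.04 = 16 REGN2222 infants, selected by an outcome that treatment is meant to change.

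**(d) All visits except those of the initial episode, follow-up from first dose.** With a 14-day episode (assumed), expected countable days per infant are 150 − 0.04·14 = 149.44 and 150 − 0.10·14 = 148.6. RR = 149.44/148.6 = 1.006, or exactly 1 if episode days are also removed from follow-up.

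**Sampling variation.** I simulated 400 per arm with uniform onset, 14-day episodes, 4 visits per year and gamma frailty of variance 1, all assumed. Pooled rate ratios, median and 95% range:
- (a): 0.38 (0.09 to 1.15)
- (c): 0.99 (0.29 to 2.49)
- all-infant count, with infected infants followed only after their episode: 1.00 (0.83 to 1.20)

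In a separate run only 70 of 300 negative binomial fits under (a) were usable, so I rely on pooled ratios.

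**A related gap.** The item 14 formula reduces to end date minus stop date. It is zero or negative when the episode ends at or after the last visit. It has no value for an ongoing episode if the stop date comes from the linked adverse event, because SAP 6.3 plans no imputation of resolution dates.

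**The case against.** The strongest reply is that a clock starting after an RSV episode makes sense only for infants who had one. On that reading the zero rule covers infected infants with no later visit, RSV-free infants contribute nothing, and no artefact arises. The text permits this, so a reader who infers that the analysis will necessarily produce a 60% reduction goes beyond the SAP: it specifies neither full follow-up for RSV-free infants nor a model without an offset. What remains is that the SAP does not choose, and the infected-only reading has its own defect, the post-randomisation subset.

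It can also be said that post-RSV visits per randomised infant is a legitimate comparison of burden. That is fair. The difficulty is the label, since such a figure mixes RSV prevention with later visits and shows a reduction even when later-visit rates are equal.

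The 10% and 4% are rates for the primary endpoint, hospitalisation or outpatient LRTI. Item 14 refers to RSV illness without that limit, and neighbouring items count upper or lower infection. The documents give no planning rate for the wider set, so the 60% and the 40 and 16 infants are illustrations. This objection stands.

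Finally, items 9 to 12 already give all-cause respiratory visits with follow-up from first dose, so total burden is visible without item 14. That limits the harm but does not make item 14 interpretable.

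**Conclusion.** The point holds as a specification defect with material consequences for one exploratory endpoint. An unstated programming choice moves the expected estimate from no reduction to about 60% when the drug has no effect on later visits. The 60% is conditional on RSV-free infants being kept as zeros, with 150-day follow-up or no offset, and on the primary-endpoint planning rates. More generally the artefact tracks the effect on whichever RSV-episode definition is used. With 400 per arm any single estimate would be imprecise.

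Item 14 also departs from protocol 8.4 in two ways: it counts only visits after the episode, and only respiratory-illness visits where the protocol says medical visits. SAP 1.2.3 declares neither.

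A reader might infer a threat to the trial's efficacy conclusions. The documents do not support that: the endpoint is exploratory, its p-values are descriptive, and the primary and secondary tests are unaffected.

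**What to change.** Before database lock, redefine item 14: for every infant in the full analysis set, count visits over the whole efficacy period except those of the initial RSV episode, with follow-up from first dose. State which RSV episode definition applies, that log follow-up is the offset, and whether the days of the initial episode are removed from follow-up.

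Either use the protocol's medical visits or declare the restriction to respiratory-illness visits in SAP 1.2.3. The declared restriction may be the practicable choice, because protocol 6.5 asks for the additional visit information only where the infant had a medically attended respiratory infection.

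If post-RSV visits are also wanted, summarise them descriptively among infected infants, including those with no later visit, and report no relative risk reduction. Give a rule for episodes that are ongoing or end at the last visit.

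The cost is SAP wording and a recount of visit data already collected.

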5.7.5. Other Exploratory Analyses

5.7.5.1. Potentially Pre-incubated RSV infection Prior to Study Treatment

Subjects who had their primary endpoint event occurrence by study day 7 (study day 1 being the day when the first dose of study drug was administered) could have potentially already contracted the RSV infection before receiving study drug. To assess the sensitivity of efficacy results to those potentially pre-incubated RSV infections, such subjects will be considered as having no primary endpoint unless the subject had another primary endpoint event with onset more than 7 days after the first dose during the study (ie, on or after study day 8). In this sensitivity analysis, for ET subjects who did not complete Day 150 visit, their missing endpoint will be handled according to the same rules as used in the primary analysis for the primary efficacy variable (Section 4.6.1), however, all primary endpoint event occurrences by study day 7 will neither be included as events in the construction of KM estimate nor be considered as events in the analysis of treatment effect using the CMH statistics.

5.7.5.2. RSV Subtype Analysis

The primary endpoint and its component endpoints (as described in Section 5.7.1.4) will be summarized for each RSV subtype (ie, subtype A and subtype B, respectively) by treatment

group. Only **observed** primary endpoint events with **available** RSV subtype information will be included as events in this analysis. Treatment effect of each REGN2222 arm (over placebo) in prophylaxis against each RSV subtype will be assessed using CMH statistics with randomization stratum adjusted by the MH method previously described in 5.7.1. Confidence intervals will be provided only for exploratory purpose.

5.7.5.3. Non-RSV Medically Attended Respiratory Illness

To evaluate the effect of REGN2222 on the non-RSV MARI, the proportion of subjects who had medically attended respiratory illness (hospitalization or outpatient LRTI) not confirmed to be related to RSV (either all negative RSV or missing RSV testing results within 14 days since AE onset) will be summarized for each treatment group. If a subject had both non-RSV MARI and RSV MARI (ie, the primary endpoint event), they will not be included in the numerator when calculating the proportion. For this particular analysis, only observed events will be included as events. Treatment difference in this proportion will be summarized using descriptive statistics.

